#### **13.4 Data Safety Monitoring Board**

An independent Data Safety Monitoring Board (DSMB) will be established to review the safety of the LUM Imaging System and to review any SAEs that occur during the study. The DSMB will develop and follow a DSMB Charter. The DSMB will be composed of at least 2 oncology specialists (at least one of whom specializes in surgical oncology) and a statistician. The DSMB will be provided with all reports of adverse events including SAEs regardless of investigator causality assessments.

Following the initial meeting, DSMB meetings will occur on a periodic basis in accordance with the DSMB charter. The chairperson of the DSMB will also be immediately provided with the report of any SAE that is judged as possibly, probably, or definitely attributable to treatment with the investigational product. The charter of the DSMB will specify that this committee is charged with providing periodic reports to Luminicell that contain recommendations that include, but are not limited to, (a) continuation of the study, and (b) termination of the study.

### **14 REGULATORY CONSIDERATIONS**

#### **14.1 Protocol review and amendments**

This protocol, the proposed informed consent and all forms of subject information related to the study (e.g., advertisements used to recruit subjects) and any other necessary documents must be submitted, reviewed and approved by a properly constituted IRB governing each study location.

Any changes made to the protocol must be mutually agreed upon by Luminicell. Such changes must be submitted as amendments and must be approved by the IRB prior to implementation. Any changes in study conduct must be reported to the IRB. Luminicell will disseminate protocol amendment information to all participating investigators.

All decisions of the IRB concerning the conduct of the study must be made in writing.

In addition, any modifications to the protocol, consent or case report forms will be submitted to the FDA.

#### **14.2 Informed consent**

All subjects must be provided a consent form describing this study and providing sufficient information for subjects to make an informed decision about their participation in this study. The formal consent of a subject, using the current IRB approved consent form, must be obtained before any study-related procedures are performed. The consent form must be signed and dated by the subject or the subject's legally authorized representative, and by the person obtaining the consent. The subject must be given a copy of the signed and dated consent document. The original signed copy of the consent document must be retained in the medical record or research file.

#### **14.3 Ethics and Good Clinical Practice (GCP)**

LUMICELL CONFIDENTIAL

This document is confidential. Do not disclose or use except as authorized.

This study is to be conducted according to the following considerations, which represent good and sound research practice:

- E6 Good Clinical Practice: Consolidated Guidance
- US Code of Federal Regulations (CFR) governing clinical study conduct and ethical principles that have their origin in the Declaration of Helsinki
  - Title 21 Part 11 – Electronic Records; Electronic Signatures
  - Title 21 Part 50 – Protection of Human Subjects
  - Title 21 Part 54 – Financial Disclosure by Clinical Investigators
  - Title 21 Part 56 – Institutional Review Boards
  - Title 21 Part 812 – Investigational Device Exception Application
- State laws
- Institutional research policies and procedures
- Contractual agreements

It is understood that deviations from the protocol should be avoided, except when necessary to eliminate an immediate hazard to a research subject. In such case, the deviation must be reported to the IRB according to the local reporting policy.

#### 14.4 Study documentation

The investigator and all designees must prepare and maintain adequate and accurate case histories designed to record all observations and other data pertinent to the study for each research subject. This information enables the study to be fully documented and the study data to be subsequently verified.

Original source documents supporting entries in the case report forms include but are not limited to hospital records, clinical charts, laboratory and pharmacy records, recorded data from automated instruments, microfiches, photographic negatives, microfilm or magnetic media, and/or x-rays.

##### 14.4.1 Study documentation practices

- a) The investigator must maintain adequate records to enable the conduct of the study to be fully documented
- b) All records, including electronic forms, must be filled out completely. Complete each space or blank. If there is no information to go into a space or blank, then use the symbol “N/A”. If an entire section or page of a record is “N/A”, it is acceptable to indicate this by drawing one line through the entire section/page and use “N/A” near that line. It is acceptable to check a box marked “N/A” to indicate that a section or an entire page is not applicable. The use of ‘White-Out’ or similar correction fluid is forbidden.
- c) Handwritten dates are always to be recorded in the sequence of the month, day and year (mm/dd/yy or yyyy) unless otherwise specified.
- d) Use of highlighters on records is acceptable so long as the highlighter color does not obscure the underlying text if the record is copied.
- e) Accuracy is required. Always verify entries are correct and consistent with other information.
- f) Signatures are to be authentic.

LUMICELL CONFIDENTIAL

This document is confidential. Do not disclose or use except as authorized.

- g) Recorded dates are to be the actual dates in which the activities were recorded. Back-dating is forbidden.
- h) If drinks or chemicals are spilled on original records, dry them off to the best of your ability, make an immediate photocopy and make a notation of the event on the copy. Retain the original record except in the event of contamination with a hazardous material.
- i) All forms must be filled out using non-erasable pen and must be legible. The use of blue or black ink is preferred.
- j) Errors must be crossed out with a single line, the correction inserted, and the change initialed and dated by the approved person making the correction. The reason for the correction must be stated.

#### 14.5 Records retention

All study-related documents must be retained for the maximum period required by applicable federal regulations and guidelines, institutional policies or contractual agreement between Lumicell and the participating institution.

### 15 STATISTICAL CONSIDERATIONS

The objectives for expanding the Feasibility Study into Phase C at multiple sites are to:

- Collect data to refine and verify the tumor detection algorithm
- Complete hands-on training of the surgeons and clinical staff that will be participating in the pivotal study to evaluate the efficacy and safety of the LUM Imaging System in breast cancer surgeries
- Identify and address any site-specific or user-specific issues for using the LUM Imaging System in breast cancer surgeries
- Collect safety and efficacy data

#### 15.1 General methods

In addition to documenting the training status of the clinical staff on the LUM Imaging System, data from this study will be used to continue refining the tumor detection algorithm. For categorical variables, summary tabulations of the number and percentage of patients within each category (with a category for missing data) of the parameter will be presented. For continuous variables, the number of patients, mean, median, standard deviation, minimum, and maximum values will be presented.

Each data value for all the included patients will be presented using patient data listings, sorted by patient number, unless otherwise specified.

All data summary tabulations will be presented by study site and for the overall study population, as appropriate.

##### 15.1.1 Disposition of subjects

LUMICELL CONFIDENTIAL

This document is confidential. Do not disclose or use except as authorized.

Demographic and baseline characteristics data will be summarized for all patients. The total number of patients screened, enrolled, completed and reason for termination will also be summarized.

## 15.2 Sample size

Analyses during the Phase C study may lead to a change of algorithm (i.e., refinement of the threshold). The tumor detection algorithm will be locked in place before the start of the pivotal study based on the results of this Phase C study. The tumor detection algorithm lock will be contingent on the accrual of enough “pathology positives” to yield a ~7% margin of error in sensitivity. “Pathology positive” is defined as an imaged surface that contains cancer as identified by histopathology. A single patient may give more than one “pathology positive” image. Given that 19 pathology positive samples were acquired during the Phase B study, an additional 32 pathology positives will be needed to achieve the targeted margin of error. Because 40 patients in the Phase B study yielded 19 pathology positives, we expect to image approximately 67 patients during the training portion of the pivotal study (Phase C) before locking the threshold algorithm in place for the pivotal study. However, because the incidence of pathology positives is largely unknown at the sites participating in the future pivotal trial, the study will continue until enough patients have been enrolled to collect the data to lock the tumor detection algorithm. This number of patients will not exceed 250 patients.

Based on our experience from Phase A and Phase B of the feasibility study, we anticipate that with up to 5 patients per surgeon and approximately 1-3 surgeons per site, we may identify and address any site-specific and surgeon-specific issues related to the use of the LUM Imaging System. We anticipate expanding the study to a maximum of 20 sites; thus, we expect to have up to 250 patients in Phase C.

If tumor detection algorithm verification is complete, yet not all surgeons and clinical staff have completed training on the LUM Imaging System, these institutions can continue the training process as a lead-in to any Luminell Imaging Studies they may participate in the future.

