The LUM Imaging System has been tested in a two-phases of the Feasibility Study at the Massachusetts General Hospital. Fifteen patients in Phase A and 45 patients in Phase B were included in the study. The results indicate zero false negatives in the margin cavity walls and avoidance of two second surgeries based on the detection of positive signal with the LUM Imaging Device. These results are presented in the Phase B report.

This experience showed that user related issues are not easily identified until the surgeon uses the system in the clinical setting. No amount of "dry runs" outside the operating room reveal the important issues that arise during surgery; for example, optimizing a surgeon's approach for keeping the hand-held unit in contact with the tissue, thorough scanning of the cavity walls, and co-location of the image with the additional shaved margin tissue to be removed. Therefore, we believe that it is critical to introduce the LUM Imaging System into additional clinical sites and train the clinical staff prior to the pivotal study.

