## 5 STUDY DESIGN

### 5.1 Overview and background

Phase A and Phase B of the Feasibility Study were conducted at the Massachusetts General Hospital (MGH). Data from these studies were used to develop the Lumicell tumor detection algorithm that is implemented in the Lumicell decision software. Phase A included 5 subjects not injected with LUM015 for assessment of tissue autofluorescence and 10 subjects receiving LUM015 (5 subjects at a dose of 0.5 mg/kg and 5 subjects at a dose of 1.0 mg/kg) to assess the ability to distinguish LUM015 from autofluorescence. Phase A concluded with the analysis of the data to (1) assess patient safety, (2) determine initial parameters for the tumor detection algorithm and (3) select the dose of 1.0 mg/kg for Phase B. In Phase B, the tumor detection algorithm was fine-tuned for in vivo detection of residual cancer to guide the resection of additional shaved cavity margins (SCMs), known as therapeutic shaves. There were zero false negatives in the margin cavity and two second surgeries were avoided because the surgeon removed additional shaves guided by the LUM Imaging System that converted a positive margin into a negative one. The detailed results are presented in the Phase B Report.

Two of the three surgeons participating in Phase B requested an optical head with a smaller diameter because the incisions they typically make are too small for the optical head with a 3.1 cm outer diameter to fit. For Phase B, these two surgeons opted to make a larger incision than usual to fit the LUM Optical Head. In response to this request, Lumicell designed and built a smaller

LUMICELL CONFIDENTIAL

This document is confidential. Do not disclose or use except as authorized.

diameter distal end for the LUM Optical Head; however, the smaller version was not used in Phase B because the study was completed prior to obtaining IRB approval for using this version of the LUM Optical Head in the operating room.

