## 15.5 Efficacy and intraoperative imaging data analysis

LUMICELL CONFIDENTIAL

This document is confidential. Do not disclose or use except as authorized.

The tumor detection algorithm optimized during Phase B will be implemented in Phase C to guide the resection of therapeutic SCMs. The imaging data will be compared against histopathology analysis of resected tissue on the side of the tissue where in vivo imaging took place. The data obtained from the different surgeons at each site will be used to further train the tumor detection algorithm. The combined algorithm training data from Phase B and Phase C will be used to estimate the expected results in the pivotal trial to properly power that study.

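### The ~7% margin of error behind the algorithm lock (Protocol 15.2) depends on unstated inputs, and the sensitivity interval makes no adjustment for correlated tissues of one patient

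*Protocol*

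**What the plan says.** Protocol 15.2 makes the lock contingent on accruing enough pathology positives "to yield a ~7% margin of error in sensitivity". It credits 19 positives from 40 Phase B patients, states that "an additional 32 pathology positives will be needed to achieve the targeted margin of error", and projects about 67 patients to obtain them. Because the incidence of positives at the new sites is largely unknown, "the study will continue until enough patients have been enrolled to collect the data to lock the tumor detection algorithm", up to 250 patients. The section states no expected sensitivity, confidence level or interval method. It defines a pathology positive at the level of an imaged surface and adds that "A single patient may give more than one" such image.

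SAP 3.3.2 measures sensitivity per tissue. SAP 4.3 takes it from the 2x2 table with a two-sided 95% interval and names no method for that interval. SAP 4.8.2 combines several images of one orientation or shave into a single result. Nothing in either document deals with correlation between different orientations or shaves of the same patient.

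**The concern.** A margin of error for a proportion has no fixed value until the proportion, the confidence level and the method are given. All three are missing from Protocol 15.2, so a reader cannot tell when 51 positives deliver 7 points and when they do not. This matters because the figure is the stated condition for freezing the algorithm, and Protocol 15.5 uses the combined Phase B and Phase C data to power the pivotal study.

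The second issue is the unit of analysis. Tissues from one patient share a cavity and, under Protocol 4.5, a detection threshold set from that patient's own initial images. Correlation within a patient is therefore plausible. If it is positive, an interval that counts each tissue as independent overstates the precision of sensitivity, whatever number of positives is reached.

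**Working it through.** **Inputs.** From Protocol 15.2: 19 positives in 40 Phase B patients, 32 more needed, target ~7%, about 67 patients, cap 250. From SAP 4.3: two-sided 95%. Assumptions, because the documents give no value: sensitivity between 80% and 95%, a Wald interval, independent tissues, and later a design effect.

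**1. Reproduce the plan's figures.** 19 + 32 = 51 positives, and 32 / (19/40) = 67.4 patients, as printed. For a Wald half-width h, n = z²p(1−p)/h². With p = 0.93 and h = 0.07, n = 1.96² × 0.93 × 0.07 / 0.07² = 51.04. Two other routes also lead to 51:
- 90% Wald at 89.7% sensitivity: 1.645 × √(0.897 × 0.103 / 51) = 7.0 points.
- Exact 95% lower limit with zero misses: 1 − 0.025^(1/51) = 6.98 points. With 50 positives it is 7.11, so 51 is the smallest number under 7.

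The figure is reproducible, but its origin cannot be determined.

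**2. Dependence on sensitivity.** 95% Wald half-width, 1.96 × √(p(1−p)/51):

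| Sensitivity | 95% | 93% | 92% | 90% | 85% | 80% |
|---|---|---|---|---|---|---|
| Half-width (points) | 6.0 | 7.0 | 7.5 | 8.2 | 9.8 | 11.0 |

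Protocol 3.2 and 5.1 report for Phase B that "There were zero false negatives in the margin cavity". If this covers all 19 positives (an assumption), the exact lower limit is 0.025^(1/19) = 82.4%. Values of 85% to 90% are then not excluded, but neither are they what Phase B suggests.

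**3. Dependence on method.** With few misses, the method decides whether 7 points appears to be met:

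| Result | Wald half-width | Wilson half-width | Exact half-width | Exact lower arm |
|---|---|---|---|---|
| 51/51 | 0 | 3.5 | 3.5 | 7.0 |
| 50/51 | 3.8 | 5.0 | 5.2 | 8.5 |
| 48/51 | 6.5 | 7.0 | 7.5 | 10.4 |

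**4. Correlation within patients (illustration only).** Design effect d = 1 + (m−1)ρ. With m = 2 positives per contributing patient and ρ = 0.2, 0.5 or 1.0, d = 1.2, 1.5 or 2.0. The Wald half-width is multiplied by √d:

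| d | 93% | 90% | 85% |
|---|---|---|---|
| 1.0 | 7.0 | 8.2 | 9.8 |
| 1.2 | 7.7 | 9.0 | 10.7 |
| 1.5 | 8.6 | 10.1 | 12.0 |
| 2.0 | 9.9 | 11.6 | 13.9 |

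With zero misses, the exact lower limit 0.025^(d/51) falls from 93.0% at d = 1 to 91.7%, 89.7% and 86.5%.

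**5. Patients needed if a 7-point half-width governs.** Patients = (positives − 19) / (19/40), rounded up, with independent tissues. Exact limits are evaluated at the expected, possibly non-integer, number of detections.

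| Sensitivity | Wilson: positives, patients | Exact: positives, patients |
|---|---|---|
| 93% | 57, 80 | 65, 97 |
| 90% | 73, 114 | 84, 137 |
| 85% | 100, 171 | 113, 198 |
| 80% | 124, 222 | 138, 251 |

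For example, (57 − 19) / 0.475 = 80. The last exact entry exceeds the cap of 250. Clustering raises every entry.

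**The case against.** The strongest reply is that Protocol 15.2 already works as a precision criterion. The lock depends on reaching ~7%, the 32 is derived from that target, 67 is only approximate, and enrolment stays open to 250. That largely stands. A reader might infer that the lock is a fixed count of 51 and is bound to miss its target, but the text does not support this. What remains is that no width, level or method is named by which reaching ~7% could be judged.

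A reader might also infer that ~7% is an arithmetic error. It is not: three sets of inputs reproduce it. The 95% level is itself borrowed. It comes from the SAP, whose hierarchical truth standard is not worded like the definition of a pathology positive in 15.2. At 90% confidence and 90% sensitivity, 51 positives give 6.9 points. This limits how much weight any one column of the figures can carry, but not the finding that the result is conditional.

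Nor can it be said that the documents overlook several positives from one patient. The protocol mentions them, and SAP 4.8.2 merges images within an orientation or shave. The gap is narrower: correlation between different tissues of one patient. The design effects above are illustrative, and 2.0 would need two perfectly concordant positives from every contributing patient.

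Finally, this is a training and feasibility phase, and the SAP introduction says that the protocol pre-defined no hypothesis-tested endpoints. That lowers the stakes. It does not justify an interval that may be too narrow, since the data feed the pivotal study's power.

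**Conclusion.** The point holds in a limited form. The ~7% is correct under inputs that Protocol 15.2 leaves out. Under 95% Wald with independent tissues, it is 7.0 points at 93% sensitivity and rises to 11.0 at 80%. The planning value behind 51 cannot be recovered from the documents, and sensitivities below 93% are scenarios, not expectations.

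The per-tissue interval in SAP 4.3 will be too narrow if tissues of one patient are positively correlated. How much too narrow is unknown, because the documents give neither an intra-patient correlation nor a number of positives per contributing patient.

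It would also go too far to conclude that about 67 patients suffice at 93%, or that the cap always leaves room. Both depend on the interval chosen, as step 5 of the working shows. The changes should be made, but the omissions do not invalidate the study.

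**What to change.** 1. In SAP 4.3 and at the lock, replace the per-tissue interval with a patient-clustered two-sided 95% interval that remains valid with zero or few misses. One option is a Wilson or exact interval on a sample size divided by the design effect. With zero misses the design effect cannot be estimated from the data, so fix a value in advance for that case.
2. Restate Protocol 15.2 along these lines: *With 51 pathology positives treated as independent, the two-sided 95% Wald half-width for sensitivity is 7.0 points if sensitivity is 93%, 8.2 at 90%, 9.8 at 85% and 11.0 at 80%. Correlation between positives from one patient widens these figures.*
3. State that the existing ~7% criterion means the half-width of the interval named in item 1, and that 32 positives and 67 patients are planning figures.

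**Cost.** Wording in both documents, slightly more analysis, and a stated precision that looks less favourable. The restatement itself needs no extra patients. If the sponsor chooses to enrol until the 7-point half-width is met, the expected numbers (independent tissues, Phase B yield of 19/40) are about 80 (Wilson) or 97 (exact) at 93% sensitivity, 114 or 137 at 90%, 171 or 198 at 85%, and 222 or 251 at 80%. The last figure is above the cap, and clustering adds to all of them. If that enrolment is not wanted, keep 51 and report the precision actually achieved, without describing it as 7% unless it is.

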## 15.3 Populations for analysis

Safety evaluations will be based on all patients who enter the study that are injected with LUM015, regardless on whether the LUM Imaging Device was used for intraoperative imaging (there may be subjects injected with LUM015 and not imaged intraoperatively for a variety of reasons). Subjects imaged with the LUM Imaging System will be included in the analysis of the imaging data unless otherwise specified.

## 15.4 Exclusions

Subjects injected with LUM015 but not imaged with the LUM Imaging Device will not be included in the analysis of the imaging data and will not count towards the 3 patients per surgeon to complete the training. They will be included in the safety analysis. Other subjects excluded from any analysis will be indicated with a rationale as to why the patient was excluded.

## 15.5 Efficacy and intraoperative imaging data analysis

LUMICELL CONFIDENTIAL

This document is confidential. Do not disclose or use except as authorized.

The tumor detection algorithm optimized during Phase B will be implemented in Phase C to guide the resection of therapeutic SCMs. The imaging data will be compared against histopathology analysis of resected tissue on the side of the tissue where in vivo imaging took place. The data obtained from the different surgeons at each site will be used to further train the tumor detection algorithm. The combined algorithm training data from Phase B and Phase C will be used to estimate the expected results in the pivotal trial to properly power that study.

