#### 4.5 LUM decision software

LUMICELL CONFIDENTIAL

This document is confidential. Do not disclose or use except as authorized.

The LUM Imaging System is powered by Lumicell's proprietary decision software. The decision software uses an initial set of images acquired from the lumpectomy cavity after the main specimen is removed to set the tumor detection threshold. Then, while the surgeon scans the lumpectomy cavity walls with the LUM Optical Head, the decision software compares the intensity of an image against the tumor detection threshold and identifies whether a region of the image is suspected to contain tumor. Regions with fluorescence signal above the threshold are highlighted in the computer monitor for the surgeon to see in real-time; that is, there is no delay between the scanning of a region and the display of the results from that region. **Figure 3** shows the user interface and what the surgeon sees during scanning of the cavity walls. The decision software was developed and optimized during Phase A and Phase B of the Feasibility Study in breast cancer patients.

**Figure 3:** Screen shot of the user interface for the LUM decision software. Regions highlighted in red indicate areas suspected to have tumor.

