We also refined our training process to highlight information that surgeons found important for using the LUM Imaging System comfortably and as intended. Examples of areas addressed during user training include: (1) making sure that the device is in contact with the tissue being scanned, (2) translating the region identified by the decision software as having cancer into the actual location of the shave to be removed once the LUM Optical Head is out of the cavity, (3) ensuring that the naming of the therapeutic shaves for pathology analysis matches the naming of the Luminicell images, and (4) selecting the proper size of the LUM Optical Head to be used for a given surgery.

The primary objective of this Phase C study is to further refine and verify the algorithm used for detection of residual cancer tissue. The secondary objective is to implement learning from Phases A and B of the Feasibility Study at MGH, in particular, training of breast cancer surgeons and hospital staff at the different sites. We are planning to include up to 20 sites participating in Phase C with approximately 1-3 surgeons at each site. In Phase C, a uniform method for orienting and inking the main specimen will be implemented prior to the subsequent pivotal study (see Appendix B).

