## 8.2 Imaging of the lumpectomy cavity walls and shaved cavity margins

For Phase C, the surgeon will perform the lumpectomy procedure according to his or her institution's standard of care practice as outlined in sections 5.4.1 to 5.4.3. After the standard of care procedure, the surgeon will have the option of using the LUM002 or the LUM003 depending on their preference and their assessment of likely incision and surgical cavity dimensions. Following the standard of care procedure, the surgeon will image the tumor bed in order to establish a normal tissue baseline for the thresholding algorithm. With the thresholding algorithm applied, the surgeon will then remove therapeutic shaves based on the recommendation of the LUM Imaging System. The surgeon will be limited to removing no more than 2 therapeutic shave for a given orientation (see section 5.3 for definitions of orientations). If the surgeon decides to take a different action than the one suggested by the LUM Imaging System, this is considered a protocol deviation. The surgeon must notify the computer operator or clinical coordinator for documenting the reason for not following the study procedures in the study worksheets. The

LUMICELL CONFIDENTIAL

This document is confidential. Do not disclose or use except as authorized.

surgeon has the option to record an image from the final cavity after the 2 therapeutic shaves are removed.

Also, ex vivo images of the non-margin side of shaved cavity margins will be recorded in the operating room after the in vivo portion of the imaging session is completed.

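### Protocol 15.5 takes the expected pivotal performance from the data that train the algorithm, with no stated optimism correction

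*Protocol*

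**What the plan says.** Protocol 5.1 sets the task: "The primary objective of this Phase C study is to further refine and verify the algorithm used for detection of residual cancer tissue". The algorithm enters Phase C already tuned: "In Phase B, the tumor detection algorithm was fine-tuned for in vivo detection of residual cancer". Section 15.5 starts Phase C with the Phase B version, compares the images with histopathology, and continues: "The data obtained from the different surgeons at each site will be used to further train the tumor detection algorithm". The next sentence gives the same data a second use: "The combined algorithm training data from Phase B and Phase C will be used to estimate the expected results in the pivotal trial", so that the pivotal trial can be powered.

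Section 15.2 lets analyses during Phase C change the threshold. It makes the algorithm lock depend on enough pathology-positive images for a margin of error of about 7% in sensitivity. Phase B supplied 19 of these, and "an additional 32 pathology positives will be needed to achieve the targeted margin of error".

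Two passages describe how the threshold works in the operating room. In 4.5 the software uses an "initial set of images acquired from the lumpectomy cavity after the main specimen is removed to set the tumor detection threshold". In 8.2, "the surgeon will image the tumor bed in order to establish a normal tissue baseline for the thresholding algorithm".

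Neither document gives the rule for choosing the cut-off, says which data refine and which verify, or describes an out-of-sample or optimism-corrected estimate. SAP 4.3 gives a 2x2 table with point values and 95% confidence intervals. SAP 4.8 lists summaries for the whole study, by device size and by site, but not by algorithm version.

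**The concern.** A cut-off chosen because it does well on a set of labelled images looks better on those images than it will on new ones. If the pathology positives take part in the choice, sensitivity computed on the same positives is optimistic in expectation, and the error always runs in the favourable direction. Section 15.5 sends that figure into the design of the next trial.

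The stake is the realism of the pivotal planning figures. The stated primary objective also includes verification, and the plan does not set any reads aside for that purpose.

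**Working it through.** **1. The plan's own figures.** Yield in Phase B is 19/40 = 0.475 positives per patient, so 32 more positives need 32/0.475 = 67.4 patients, which agrees with the approximately 67 in 15.2. The total is 19 + 32 = 51. No sensitivity or confidence level is stated for the 7% margin. With a 95% Wald interval it is reproduced at an assumed sensitivity of 0.93:

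1.96 × √(0.93 × 0.07/51) = 0.070.

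**2. Rules that use only the ranks of the positives.** These need no signal model, only independent images. If the cut-off is the j-th lowest signal among n positives, apparent sensitivity is (n − j + 1)/n and expected sensitivity in new positives is (n − j + 1)/(n + 1).

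- No missed positive (j = 1, n = 51): 51/51 = 100% against 51/52 = 98.1%, an excess of 1.9 points.
- At least 90% sensitivity (j = 6): 46/51 = 90.2% against 46/52 = 88.5%, an excess of 1.7 points.

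**3. Other rules, by simulation.** Assumptions: 51 positives, 600 negatives, normal signals with means d standard deviations apart, independent images, one tuned cut-off, 4,000 data sets per setting. Entries are apparent minus true sensitivity, in points.

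| Rule for the cut-off | d = 1.5 | d = 2.0 | d = 2.5 |
|---|---|---|---|
| Maximum Youden | 4.88 | 4.04 | 3.62 |
| No missed positive | 1.95 | 1.90 | 1.95 |
| At least 90% sensitivity | 1.85 | 1.64 | 1.74 |
| At least 80% specificity (normal tissue only) | 0.19 | 0.00 | 0.11 |

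A second simulation allowed for clustering within patients (correlation 0.15, six orientations per patient) and subtracted a baseline estimated from five initial images. For d from 1.5 to 3 it gave 3.5-5.2 points for maximum Youden, 1.9-2.1 for the two sensitivity-based rules, and −0.1 to 0.2 for rules set on normal tissue.

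**4. More than one variant.** If 5-10 correlated algorithm variants are also compared on the same 51 positives by maximum Youden, the excess is about 6-9 points. Five points is therefore not a ceiling.

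**5. Specificity.** The excess depends on the number of negatives, which the documents do not give. For maximum Youden at d = 1.5 it is about 0.3 points with 591 negatives, 0.9 with 200 and 1.3 with 150.

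**6. Scale.** At 0.93 with 51 positives the standard error is 0.070/1.96 = 3.6 points, so an excess of 2-5 points is about 0.6-1.4 standard errors.

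**7. Phase C reads alone.** With 32 positives the half-width is 1.96 × √(0.93 × 0.07/32) = 8.8 points, against 7.0 for the pooled 51.

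**The case against.** **Section 15.5 names a data source, not an estimator.** Cross-validated and bootstrap estimates are also computed from training data. This stands in part: a reader might infer that the sponsor will use uncorrected figures, and the documents do not say so. They do not rule it out either, and one sentence would.

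**The bias may be zero.** Sections 4.5 and 8.2 describe a threshold calibrated on each patient's own cavity. That is possible but not shown. Those passages describe calibration at the time of use and do not exclude a common parameter tuned on labelled positives. Section 15.5 puts the histopathology comparison directly before the further training, and 15.2 ties the lock to the count of positives.

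**Out-of-sample data already exist.** This stands. Phase C begins with the Phase B version, and a live read precedes that patient's pathology, which by Protocol 3.2 often takes 7-10 days. Her labels therefore cannot have set the version that read her. A reader might infer that the SAP's 2x2 table is itself inflated by tuning. If it uses live calls, it is not; at worst it mixes versions. SAP 3.3.2 and 4.8.3 fit the live reading, but the SAP does not state it, and neither document reserves these reads for verification.

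**The excess is below the 7% margin of error.** True at the sizes shown for one tuned cut-off, but the margin describes random error around the estimate, whereas optimism moves its centre.

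**Conclusion.** The point holds as a planning weakness. The data that train the algorithm are also the stated source of the expected pivotal results, and no correction is specified. With about 51 positives and one tuned cut-off, sensitivity would be overstated by about 2 points under a no-miss or fixed-sensitivity rule and by 3-5 points under maximum Youden. The excess is about zero if only normal tissue sets the cut-off, and larger if variants are compared. Specificity would be overstated by about 0-1.3 points. Apart from the rank-based results, these sizes depend on assumed signal separations and numbers of negatives, and all of them depend on an unstated rule. Confidence is high that training data are the planned source, and moderate to low for the size.

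A reader might infer that the pivotal study is underpowered or its results biased. The documents support neither. The pivotal power calculation is not in them, and any discounting in the pivotal protocol that the SAP cites (CL0007r07) cannot be seen. The algorithm is locked before that study and tested there on new patients.

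**What to change.** In Protocol 15.5, replace the last sentence with:

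> Expected pivotal sensitivity, specificity and Youden Index will be estimated from the combined Phase B and Phase C data by patient-level cross-validation or bootstrap optimism correction that repeats the whole threshold-setting step. Uncorrected training-data estimates will not be used to power the pivotal study. The algorithm version in force is recorded for each cavity image.

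Repeating the step requires the cut-off rule to be written down, including whether it uses pathology positives.

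In SAP 4.3 and 4.8, state that the 2x2 table uses the real-time LUM call. If the threshold changed during Phase C, report by algorithm version as well. If it did not, present the table as verification of the Phase B version on new patients.

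State one limitation. Under SAP 3.3.2 the truth standard depends on the LUM call, because a negative image leads to no guided shave. Resampling stored images does not correct that.

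The cost is one data field, a little more analysis and slightly less favourable planning figures. Resampling keeps all 51 positives, so it avoids the wider interval that comes with planning from Phase C reads alone.
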